8.5.3 Calculation of Derivation of Pharmacokinetic Variables

Pharmacokinetic parameters will be derived using noncompartmental methods with Phoenix[®] WinNonlin[®] Version 6.4 or higher (Certata, L.P. Princeton, New Jersey, US) and/or SAS[®] Version 9.2 or higher (SAS Institute, Inc., Cary, North Carolina, US). Actual elapsed time from

dosing and baseline adjusted DPPC and CP concentrations will be used for the final serum PK parameter calculations.

Serum Pharmacokinetic Parameters

The PK parameters in [Table 6](#) will be determined for serum DPPC and CP on Day 14, when possible.

Table 6 Serum Blood Pharmacokinetic Parameters

Pharmacokinetic Parameter	Definition
C_{\max}	Maximum concentration, obtained directly from the baseline adjusted concentration versus time data.
t_{\max}	Time to C_{\max} .

Additional serum parameters may be calculated if deemed appropriate.

Drug concentration information that may unblind the study will not be reported to the study center or study personnel until the study has been unblinded.

8.6 Pharmacodynamics

Pharmacodynamic parameters are not evaluated in this study.

8.7 Genetics

Genetics are not evaluated in this study.

8.8 Biomarkers

Biomarkers are not evaluated in this study.

8.9 Health Economics

Health Economics parameters are not evaluated in this study.

9.0 STATISTICAL CONSIDERATIONS

9.1 Statistical Hypotheses

Not applicable.

9.2 Sample Size Determination

The sample size is not based on statistical considerations, but is typical for studies of this nature, and is considered adequate to characterize the distribution of the planned endpoints.

There will be a total of 30 subjects; 2 dose cohorts of 15 subjects each. Subjects will be randomized in 4:1 (OP0201:placebo) ratio to receive either OP0201 or placebo within each dose cohort.

9.3 Populations for Analyses

For purposes of analysis, the analysis sets in [Table 7](#) are defined.

Table 7 Analysis Sets

Analysis Set	Description
Entered Analysis Set	All subjects who sign the informed consent form.
Safety Analysis Set	All subjects who receive any study treatment (OP0201 or placebo). Subjects will be analyzed according to the treatment they received.
Pharmacokinetic Analysis Set	All subjects in Cohort B who received at least 1 dose of OP0201 and have 1 quantifiable serum DPPC or CP concentration collected post-dose without important protocol deviations/violations or events thought to significantly affect the pharmacokinetics.

CP = cholestryol palmitate; DPPC = dipalmitoylphosphatidylcholine

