6.3. PHARMACOKINETIC ANALYSIS SET

The pharmacokinetic analysis set will include all subjects in Cohort B who receive at least 1 dose of study drug, OP0201 or placebo, and have at least 1 quantifiable serum DPPC concentration collected post-dose without any important protocol deviations/violations or events thought to significantly affect the PK of DPPC. Subjects in this population will be used for all PK analyses and summaries.

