7.5. BASELINE

Baseline is defined as the last scheduled non-missing measurement taken prior to dosing and will

Document: Statistical Analysis Plan
Author: [REDACTED]

Version Number:
Version Date:

2.0
03APR2019

correspond to: Screening assessment for clinical laboratory; Day -1 assessment for Vital Signs; Day 1 pre-dose assessment for ECG in Cohort A, and the average of the mean triplicate ECG assessments at Day 1, 60 minutes pre-dose and Day 1, 30 minutes pre-dose for ECG in Cohort B; Screening assessment for Physical Examination; Day -1 assessment for Otoscopy, Tympanometry, and Nasal and Epipharynx Endoscopy ; and Screening assessment for University of Pennsylvania Smell Inventory Test (UPSIT) Olfactory test, and Audiology Pure Tone hearing test. However, if a subject is missing the planned baseline collection then the last non-missing evaluation prior to dosing (scheduled or unscheduled), if available, will become the baseline value.

For PK assessments, baseline serum concentration is defined as the mean of the two predose serum concentrations observed in samples collected on Day 1 prior to the first dose. If one predose sample is missing, the other Day 1 predose concentration will be used for baseline correction.

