12.2. DEVIATIONS RELATED TO PK ANALYSIS

Changes to the procedures or events, which may impact the quality of the PK data in Cohort B, will be considered important protocol deviations/events for PK and will be described within the clinical study report body text. These changes or events will include any circumstances that will alter the evaluation of the PK. Examples of important protocol deviation or event include, but are not limited to, administration of prohibited medication, sample processing errors that lead to inaccurate bioanalytical results, inaccurate dosing on the day of PK sampling, and/or non-compliance with dosing to the extent that it is expected to affect the PK objectives of the study. In the case of a significant protocol deviation or event, PK data collected during the affected treatment period will be excluded from the study results. Other changes to the procedures or events which do not impact the quality of the PK data will not be

Document: Statistical Analysis Plan
Author: [REDACTED]

Version Number: 2.0
Version Date: 03APR2019
[REDACTED]

considered significant protocol deviations. A common example of a non-significant protocol deviation is a missed blood sample or deviation from the scheduled time of blood collection at a time unlikely to affect the PK objectives. In contrast, a scheduled pre-dose sample which is erroneously collected postdose would be considered an important deviation leading to exclusion of this data point (and derived PK parameters, if appropriate) from the PK analysis.

Non-compliance with dose administration will be reviewed on a case-by-case basis to determine whether the deviation is expected to affect the PK objectives of the study.

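### SAP 12.2 gives conflicting levels of exclusion for a fault confined to one PK sample: a single data point in one sentence, the whole treatment period in another

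*Protocol*

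**What the plan says.** **Set definition.** Protocol 9.3 (Table 7) admits Cohort B subjects who received OP0201 and have one quantifiable DPPC or CP value "collected post-dose without important protocol deviations/violations or events thought to significantly affect the pharmacokinetics". SAP 6.3 has the same structure for DPPC alone, asking for "at least 1 quantifiable serum DPPC concentration collected post-dose without any important protocol deviations/violations or events" thought to matter for the PK. Both documents run all PK analyses on this set.

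**Consequence of a deviation.** SAP 12.2 names sample processing errors that make the assay result inaccurate among its examples of important deviations. Its general remedy for a significant deviation is that "PK data collected during the affected treatment period will be excluded from the study results". Later in the same section, a predose sample drawn after dosing "would be considered an important deviation leading to exclusion of this data point", with derived parameters removed where appropriate. Between the two, the section says "A common example of a non-significant protocol deviation is a missed blood sample", and it treats a timing deviation unlikely to affect the PK objectives in the same way.

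**Missing samples.** SAP 7.5 states: "If one predose sample is missing, the other Day 1 predose concentration will be used for baseline correction". SAP 16.1 judges partial data case by case. SAP 16.2 gives up a subject's parameters outright only when both Day 1 predose samples are missing.

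**The concern.** Two faults that each touch one tube, both classed as important, carry different remedies. For a processing error no specific rule is given, so the general sentence applies. The wording suits a crossover trial, where dropping a period leaves the others. In this parallel-group trial each subject has one 14-day course, so dropping the period drops the subject's on-treatment PK data. A spoiled tube could then cost more than a tube that was never drawn.

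The systemic-exposure objective rests on 12 OP0201 subjects in Cohort B. Discarding a subject's valid concentrations for one bad value wastes data from a small group. It also leaves the analysed data dependent on which sentence of SAP 12.2 the analyst follows.

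**Working it through.** **1. Which remedy applies to which one-tube fault**

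| Fault in one tube | Class in SAP 12.2 | Stated consequence |
|---|---|---|
| Processing error giving an inaccurate result | Important | None specific; general rule removes the affected treatment period |
| Predose sample drawn postdose | Important | That data point, plus derived parameters if appropriate |
| Missed sample | Non-significant | That sample only; SAP 7.5 and 16.1 keep the subject |
| Timing deviation unlikely to affect PK objectives | Non-significant | None |

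The first two rows conflict on the level of exclusion.

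**2. Do *important* and *significant* differ?** The general remedy is attached to *significant* deviations, the examples to *important* ones. SAP 12.2 calls changes that may affect PK data quality important, and says those that do not affect it are not significant. The two words therefore work as opposite sides of one division, and nothing defines a separate tier. SAP 5.3 adds a third term, *major*.

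**3. What the treatment period covers.** The Schedule of Activities gives Cohort B 7 PK samples: 2 predose on Day 1, 1 predose on Day 14 and 4 post-dose on Day 14. SAP 14 ties the treatment period to the first dose onward, which leaves out the two Day 1 samples. The visit table in SAP Appendix 1 uses the term more broadly. Either way, all 5 Day 14 samples (1 + 4) fall inside it, and without them there is no Cmax or tmax.

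**4. Does the set definition remove the subject as well?** In both documents the *without* clause follows the words about the post-dose concentration. It most naturally qualifies that concentration, so one clean post-dose value keeps the subject in. A subject-level reading is grammatically possible and is not ruled out.

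**5. Size, as illustration**

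The plan's allocation reproduces: 15 × 4/5 = 12 OP0201 and 15 × 1/5 = 3 placebo. The documents give no sample fault rate, so p below is an assumption, with tubes independent.

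P(subject has at least one faulty tube) = 1 − (1 − p)^7

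| Assumed p | P(at least one fault) | Expected of 12 OP0201 |
|---|---|---|
| 1% | 1 − 0.99^7 = 6.8% | 0.8 |
| 2% | 1 − 0.98^7 = 13.2% | 1.6 |
| 3% | 1 − 0.97^7 = 19.2% | 2.3 |

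At p = 2%, the chance that at least one of the 12 has a faulty tube is 1 − 0.98^84 = 82% (12 × 7 = 84 tubes).

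Under a sample-level rule at p = 2%, a subject leaves the set only if all four post-dose tubes fail: 0.02^4 = 1.6 × 10⁻⁷. Parameters are lost if both Day 1 predose tubes or all four post-dose tubes fail: 1 − (1 − 0.02²)(1 − 0.02⁴) = 0.0004, or about 0.005 of 12 subjects.

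The whole-subject figures are upper bounds for the assumed rates, because a predose sample drawn postdose already has a data-point rule.

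**The case against.** The strongest reply is that the plan works by sample almost everywhere. The one timing fault called important has its own data-point rule, and a specific rule ordinarily governs over a general one. Missing and partial data are kept under SAP 7.5, 16.1 and 16.2. A processing error counts only if it makes the result inaccurate. SAP 5.3 already places the determination of analysis sets ahead of unblinding. SAP 12.2 has important PK deviations described in the study report, and SAP 16.1 lists all observed concentrations. All of this stands, and it narrows the problem to processing errors and similar one-sample faults that have no rule of their own. It does not settle them, because the only sentence that reaches them is the treatment-period one.

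A reader might infer more than the documents support:

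- *That the PK set drops a subject for any important deviation.* This is one reading of an ambiguous clause, and the less natural one. The clause is also limited to events thought to affect the PK significantly.
- *That mistimed samples in general trigger exclusion.* SAP 12.2 says the reverse for timing deviations unlikely to affect the PK objectives.
- *That a predose sample drawn late costs all 7 samples.* SAP 12.2 removes that data point, and for a Day 1 sample SAP 7.5 then allows the other predose value to serve.
- *That PK confidence intervals widen, or that placebo PK summaries are lost.* SAP 7.1 and 16 plan descriptive PK statistics with no interval, and Protocol 8.5.2 says post-dose placebo samples will not be assayed. SAP 6.3 does admit placebo subjects to the set, but that discrepancy is a separate matter.

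**Conclusion.** The point holds in a limited form. SAP 12.2 does not say consistently whether a one-sample fault removes the sample or the treatment period. For a processing error, its general rule taken literally removes all of a subject's Day 14 DPPC data. This is a stated rule that conflicts with the rest of the plan, so it goes beyond missing detail. The deviation clause in Protocol 9.3 and SAP 6.3 adds a weaker ambiguity in the same direction.

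The size cannot be taken from the documents. The range of 0.8 to 2.3 of 12 OP0201 subjects rests on assumed, independent fault rates of 1% to 3% per tube and on every fault removing the subject, so it is a ceiling for those rates and not a forecast. The inconsistency itself needs no assumption. It should be corrected before the analysis sets are determined.

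**What to change.** In SAP 12.2:

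- Replace the treatment-period wording with: *the affected concentrations, and any parameter that cannot be reliably derived without them*.
- Exclude all of a subject's PK data only when the event affects all of that subject's Day 14 samples.
- Use one term, *important*, throughout.
- List each excluded value with its reason.

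In SAP 6.3, state that a subject stays in the PK set while at least one unaffected quantifiable post-dose concentration remains.

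Protocol Table 7 can stay as it is, since its more natural reading already agrees with this. That avoids a protocol amendment and any approval it would need under Protocol Appendix 2. The cost is a short SAP revision and flagging a few values individually; no new data are needed.

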9.4 Statistical Analyses

The Statistical Analysis Plan (SAP) will be developed and finalized before database lock and will describe the subject analysis sets to be included in the analyses, and procedures for accounting for missing, unused, and spurious data. This section is a summary of the planned statistical analyses of the primary and secondary endpoints.

All analyses (with the exception of PK parameter analysis), summaries, and listings will be performed using SAS software (Version 9.4 or higher).

Descriptive statistics, including the following, will be used as applicable to summarize the study data:

- Continuous variables: sample size (n), mean, standard deviation (SD), median, minimum (min), and maximum (max).
- Categorical variables: frequencies and percentages.

Individual subject data will be presented in listings.

9.4.1 Efficacy Analyses

Not applicable.

9.4.2 Pharmacokinetic Analyses

Pharmacokinetic analyses will be described in the SAP that will be finalized before database lock. All PK analyses will be performed on the PK Analysis Set.

Observed and baseline adjusted serum DPPC concentrations will be summarized by time point. Observed and baseline adjusted serum CP concentrations (if available) will be summarized by time point.

Serum DPPC PK parameters (if any) will be summarized. Serum CP PK parameters (if available) will be summarized.

9.4.3 Safety Analyses

All safety analyses will be performed on the Safety Analysis Set.

Treatment-emergent adverse events (TEAEs) are defined as AEs that first occurred or worsened in severity after administration of study treatment.

Adverse events will be coded using the Medical Dictionary for Regulatory Activities (MedDRA). For each study treatment, numbers of TEAEs and incidence rates will be tabulated by preferred term and system organ class.

Treatment-emergent AEs by maximum severity, TEAEs by relationship to study treatment, SAEs, TEAEs leading to death, and TEAEs leading to discontinuation of study treatment will be tabulated for each study treatment.

All laboratory test results, vital signs measurements, and ECG results will be summarized for each treatment group using descriptive statistics at each visit for raw numbers and change from baseline.

Test results from otoscopy, tympanometry, nasal and epipharynx endoscopy, UPSIT olfactory test, and audiology pure tone hearing test will be listed and summarized as appropriate.

Additional details will be provided in SAP.

9.4.4 Missing Data

Missing data, if any, will be described in the SAP.

9.5 Interim Analyses

No interim analysis is planned.

9.6 Safety Review Committee

After all subjects in Cohort A have completed the Day 14 visit, a SRC will review all the blinded safety data to determine whether the doses administered are safe and well tolerated and to make a recommendation to escalate to the next cohort (Cohort B) or not.

11.0 APPENDICES

Appendix 1 Abbreviations

Term/Abbreviation	Definition
AE	Adverse event
ALP	Alkaline phosphatase
ALT	Alanine aminotransferase
AOM	Acute Otitis Media
C _{max}	Maximum concentration
CRF	Case Report Form
CP	Cholesteryl palmitate
DPPC	Dipalmitoylphosphatidylcholine
ECG	Electrocardiogram
EaT	Early termination
ET	Eustachian tube
eCRF	Electronic case report form
EU	European Union
FSH	Follicle stimulating hormone
FDA	Food and drug administration
GCP	Good Clinical Practice
GMP	Good Manufacturing Processes
HL	Hearing level
HRT	Hormonal replacement therapy
IB	Investigator's Brochure
ICH	International Council for Harmonisation
ICF	Informed consent form
INR	International normalized ratio
IP	Investigational product
IEC	Independent Ethics Committee
IRB	Institutional Review Board
MDI	Metered dose inhaler
ME	Middle ear
PK	Pharmacokinetics
OM	Otitis Media
OME	Otitis Media with Effusion
RDS	Respiratory distress syndrome

SAE	Serious adverse event
SAP	Statistical Analysis Plan
SoA	Schedule of Assessments
SRC	Safety Review Committee
t_{\max}	Time to C_{\max}
TEAE	Treatment-emergent adverse event
TID	Three times a day
ULN	Upper limit of normal
US	United States
UPSIT	University of Pennsylvania Smell Inventory Test
WOCBP	Woman of childbearing potential

Appendix 2 Regulatory, Ethical, and Study Oversight Considerations

Regulatory and Ethical Considerations

- This study will be conducted in accordance with the protocol and with the following:
 - Consensus ethical principles derived from international guidelines including the Declaration of Helsinki and Council for International Organizations of Medical Sciences International Ethical Guidelines.
 - Applicable ICH Good Clinical Practice (GCP) Guidelines.
 - Applicable laws and regulations.
- The protocol, protocol amendments, ICF, Investigator Brochure, and other relevant documents (eg, advertisements) must be submitted to an IRB/IEC by the Investigator and reviewed and approved by the IRB/IEC before the study is initiated.
- Any amendments to the protocol will require IRB/IEC and regulatory authority approval, when applicable, before implementation of changes made to the study design, except for changes necessary to eliminate an immediate hazard to subjects.
- The Investigator will be responsible for the following:
 - Providing written summaries of the status of the study to the IRB/IEC annually or more frequently in accordance with the requirements, policies, and procedures established by the IRB/IEC.
 - Notifying the IRB/IEC of SAEs or other significant safety findings as required by IRB/IEC procedures.
 - Providing oversight of the conduct of the study at the study center and adherence to requirements of 21 Code of Federal Regulations (CFR), ICH guidelines, the IRB/IEC, European regulation 536/2014 for clinical studies (if applicable), and all other applicable local regulations.
- After reading the protocol, each Investigator will sign the protocol signature page and send a copy of the signed page to the Sponsor or representative ([Appendix 12](#)). The study will not start at any study center at which the Investigator has not signed the protocol.

Adequate Resources

The Investigator is responsible for supervising any individual or party to whom the Investigator delegates study-related duties and functions conducted at the study center.

If the Investigator/institution retains the services of any individual or party to perform study-related duties and functions, the Investigator/institution should ensure this individual or party is qualified to perform those study-related duties and functions and should implement procedures to ensure the integrity of the study-related duties and functions performed and any data generated.

Financial Disclosure

Investigators and sub-Investigators will provide the Sponsor with sufficient, accurate financial information as requested to allow the Sponsor to submit complete and accurate financial certification or disclosure statements to the appropriate regulatory authorities. Investigators are responsible for providing information on financial interests during the course of the study and for 1 year after completion of the study.

Insurance

The Sponsor has obtained liability insurance, which covers this study as required by local law and/or national regulations and/or ICH guidelines, whichever is applicable. The terms of the insurance will be kept in the study files.

Informed Consent Process

- The Investigator or his/her representative will explain the nature of the study to the subject or his/her legally authorized representative and answer all questions regarding the study.
- Subjects must be informed that their participation is voluntary. Subjects or their legally authorized representative will be required to sign a statement of informed consent that meets the requirements of 21 CFR 50, local regulations, ICH guidelines, Health Insurance Portability and Accountability Act requirements, where applicable, and the IRB/IEC or study center.
- The medical record must include a statement that written informed consent was obtained before the subject was entered in the study and the date the written consent was obtained. The authorized person obtaining the informed consent must also sign the ICF.
- Subjects must be re-consented to the most current version of the ICF(s) during their participation in the study.
- A copy of the ICF(s) must be provided to the subject or the subject's legally authorized representative.

Data Protection

- Subjects will be assigned a unique identifier by the Sponsor. Any subject records or datasets that are transferred to the Sponsor will contain the identifier only; subject names or any information which would make the subject identifiable will not be transferred.
- The subject must be informed that his/her personal study-related data will be used by the Sponsor in accordance with local data protection law. The level of disclosure must also be explained to the subject.
- The subject must be informed that his/her medical records may be examined by Clinical Quality Assurance auditors or other authorized personnel appointed by the Sponsor, by appropriate IRB/IEC members, and by inspectors from regulatory authorities.
- The ICF will incorporate (or, in some cases, be accompanied by a separate document incorporating) wording that complies with relevant data protection and privacy legislation.

- The Sponsor or its representative will not provide individual genotype results to subjects, any insurance company, any employer, their family members, general physician, or any other third party, unless required to do so by law.
- Extra precautions are taken to preserve confidentiality and prevent genetic data being linked to the identity of the subject. In exceptional circumstances, however, certain individuals might see both the genetic data and the personal identifiers of a subject. For example, in the case of a medical emergency, the Sponsor or representative physician or an Investigator might know a subject's identity and also have access to his or her genetic data. Also, regulatory authorities may require access to the relevant files.

Administrative Structure

The safety committee will include, at a minimum, the Sponsor's responsible physician (or designated Medical Monitor) and the Principal Investigator. The Principal Investigator and the Sponsor, when appropriate, will invite other specialist individuals to participate in the review, eg, PK scientists, statisticians, clinical specialists etc.

Medical Monitor

Dissemination of Clinical Study Data

The results of the study should be reported within 1 year from the end of the clinical study. The study will be registered on clinicaltrials.gov and appropriate reporting to ensure compliance with clinicaltrials.gov will be met.

Data Quality Assurance

- All subject data relating to the study will be recorded on printed or eCRFs unless transmitted to the Sponsor or designee electronically (eg, laboratory data). The Investigator is responsible for verifying that data entries are accurate and correct by physically or electronically signing the case report form (CRF).
- The Investigator must maintain accurate documentation (source data) that supports the information entered in the CRF.
- The Investigator must permit study-related monitoring, audits, IRB/IEC review, and regulatory agency inspections and provide direct access to source data documents.
- The Sponsor or designee is responsible for the data management of this study including quality checking of the data.

- Study monitors will perform ongoing source data verification to confirm that data entered into the CRF by authorized study center personnel are accurate, complete, and verifiable from source documents; that the safety and rights of subjects are being protected; and that the study is being conducted in accordance with the currently approved protocol and any other study agreements, ICH GCP, and all applicable regulatory requirements.
- Records and documents, including signed ICFs, pertaining to the conduct of this study must be retained by the Investigator for 15 years after study completion unless local regulations or institutional policies require a longer retention period. No records may be destroyed during the retention period without the written approval of the Sponsor. No records may be transferred to another location or party without written notification to the Sponsor.

Source Documents

The Investigator/institution should maintain adequate and accurate source documents and study records that include all pertinent observations on each of the study center's subjects. Source data should be attributable, legible, contemporaneous, original, accurate, and complete. Changes to source data should be traceable, should not obscure the original entry, and should be explained if necessary (eg, via an audit trail).

- Source documents provide evidence for the existence of the subject and substantiate the integrity of the data collected. Source documents are filed at the Investigator's study center.
- Data reported on the CRF or entered in the eCRF that are transcribed from source documents must be consistent with the source documents or the discrepancies must be explained. The Investigator may need to request previous medical records or transfer records, depending on the study. Also, current medical records must be available.

Study and Study Center Closure

The Sponsor designee reserves the right to close the study center or terminate the study at any time for any reason at the sole discretion of the Sponsor. Study centers will be closed upon study completion. A study center is considered closed when all required documents and study supplies have been collected and a study center closure visit has been performed.

The Investigator may initiate study center closure at any time, provided there is reasonable cause and sufficient notice is given in advance of the intended termination.

Reasons for the early closure of a study center by the Sponsor or Investigator may include but are not limited to:

- Failure of the Investigator to comply with the protocol, the requirements of the IRB/IEC or local health authorities, the Sponsor's procedures, or GCP guidelines.
- Inadequate recruitment of subjects by the Investigator.
- Discontinuation of further study treatment development.

Publication Policy

The Sponsor will comply with the requirements for publication of study results. In accordance with standard editorial and unethical practice. Novus Therapeutics, Inc, as the Sponsor, has proprietary interest in the study and thus will be involved in reviewing, at a minimum, any abstract or manuscript prior to submission in order to allow the Sponsor to protect proprietary information and to provide comments. For this study, authorship and abstracts or manuscript composition will reflect joint cooperation between the Investigator and Novus Therapeutics, Inc. personnel. Authorship will be 1) established prior to the writing of abstracts or manuscripts, 2) determined by mutual agreement and 3) in line with International Committee of Medical Journal Editors authorship requirements.

